8.2.2 Rescue medication

An aim of this open label study is to evaluate the safety and efficacy of Ruconest in symptomatic HAE. Therefore, it is recommended to consider administering another dose of Ruconest as a first attempt of rescue medication, which is consistent with the SPC instructions. The use of additional treatment which might interfere with the evaluation of efficacy and safety is not allowed (exclusion criterion) prior to treatment with study medication (see section 8.2.1) and after the administration of study medication for as long as possible up to 8 hours. As specified in section 10.1.3, taking such additional treatment (other than Ruconest) between the onset of the attack and prior to time of initial relief of symptoms, will qualify that attack as "treatment failure". However, appropriate and urgent medical need will not be ignored nor withheld: the use of narcotics or other standard procedures for the treatment of HAE after treatment with study medication will be allowed at the discretion of the investigator.

Situations in which the investigator may decide to install additional treatment and/or supportive measures after the administration of study medication include:

1. Clear progression of symptom severity, with or without the occurrence of symptoms at new angioedema locations.
2. Unacceptable degree of abdominal pain.
3. Symptoms indicating life is threatened (respiratory and/or cardiovascular compromise), i.e. symptoms requiring immediate additional treatment. Patients developing a life-threatening attack (e.g. a laryngeal attack with respiratory and/or cardiovascular compromise) after the administration of study medication must also be treated with any treatment procedure (including intubation, tracheostomy) deemed necessary.
4. AEs requiring specific treatment (e.g. in case of anaphylaxis).

Pain medication, anti-emetics and fluid replacement may be used in case of acute attack(s), if needed. In case of therapeutic failure, rescue therapies (such as pdC1INH) or fresh frozen plasma may be administered, according to local clinical standards.

All (escape) medications taken during acute episodes should be recorded on the CRF with indication, dose, timing and apparent response.

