## **4.1.3 Secondary Efficacy Measures**

### **4.1.3.1 Time to minimal symptoms based on Overall VAS**

The time of minimal symptoms for an attack assessed using the Overall VAS is defined as the time at which the Overall VAS score falls below 20mm for all locations where VAS Scores are recorded.

- Patients who do not have minimal symptoms during the time that they are followed-up will be censored at the last time at which an Overall VAS score is recorded. Note: If a patient was randomized but did not have any post-baseline efficacy data then they will be censored at Presentation.
- A worst-case scenario will be used to impute missing Overall VAS scores for locations. If there are 2 non-missing values either side of missing value(s) then last observation carried forward (LOCF) or next observation carried backward (NOCB) will be used to carry forward or back the largest Overall VAS. If there is only one Overall VAS followed by missing values or after missing values it will be carried forward or back. If the Overall VAS score for a location is blank at Baseline, but then the location is affected by angioedema

post-dosing, a score of 0 will be imputed for all post-baseline time-points up until the first documented Overall VAS score. The worst-case scenario method will then be applied for all subsequent missing Overall VAS scores.

- The time to minimal symptoms for patients who receive disallowed concomitant medication will be censored at the last time at which the patient had an Overall VAS score prior to their receipt of disallowed concomitant medication. If this is Presentation and hence prior to study drug administration then the time to minimal symptoms will be censored at time 0 minutes.

Time to minimal symptoms (minutes) will be calculated as:

Actual date and time of minimal symptoms (or date and time of censoring) – date and time of the Overall VAS assessment at Baseline

Time of the actual date and time of minimal symptoms will be used in the calculation.

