#### **4.1.4.5 Time to complete resolution**

In a diary, dispensed at discharge from the hospital, the patient will be asked to record the date and time at which all angioedema symptoms at all locations have resolved (complete resolution). If needed, depending on the patient's level of understanding, parents may assist in completion. During the Day 28 follow-up visit, the date and time of complete resolution of symptoms, as reported by the patient in the diary, is then recorded in the Day 28 CRF.

Time to complete resolution of all symptoms at all locations will be assessed using the answer recorded on the CRF.

- Time to complete resolution of symptoms will be defined as 'Time HAE attack resolved' on the CRF.
- Patients who do not have complete resolution of symptoms during the time that they are followed-up will be censored at 72 hours if the patient confirms that they did not have complete resolution of symptoms during the follow-up time, or at the time of discharge if the 'Date HAE attack resolved' and 'Time HAE attack resolved' on the CRF were not completed. 72 hours is chosen as this is the average length of time that swelling would be expected to subside without treatment. Note: If a patient was randomized but did not have any post-baseline efficacy data then they will be censored at Presentation.
- The time to complete resolution of symptoms for patients who receive disallowed concomitant medication will be censored at the last time the patient had an Overall VAS

score prior to their receipt of disallowed concomitant medication. If this is Presentation and hence prior to study drug administration then the time to complete resolution of symptoms will be censored at time 0 minutes.

Time to complete resolution of symptoms (minutes) will be calculated as:

Actual date and time of complete resolution of symptoms (or date and time of censoring) –  
Date and time of Study Drug Admin

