#### **6.7.4 Time to Event Analysis**

Kaplan-Meier (KM) analyses will be performed for each of the time to event endpoints (time to beginning of relief and time to minimal symptoms defined using Overall VAS, IS and TEQ, and time to complete resolution). For patients who have been treated for more than one attack, KM analyses for time to beginning of relief and time to minimal symptoms using the Overall VAS score will be repeated for first and last attacks.

Patients who did not have the event of interest will be censored at their last available assessment of that endpoint. For VAS endpoints, in most cases the last available assessment will be at 24 hours post infusion, for IS endpoints it will be 4 hours post infusion.

Additionally, for each endpoint the number and percentage of patients with the event will be presented, along with estimates of the median and quartile time to events with 95% confidence intervals.

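### Censoring attacks at disallowed medication is informative, so the Kaplan-Meier curves for minimal symptoms and complete resolution lie at or above those with rescue counted as non-response

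*SAP*

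**What the plan says.** SAP 4.1.3.1 (VAS, secondary), 4.1.4.2 (IS, exploratory) and 4.1.4.4 (TEQ, exploratory) share one rule for time to minimal symptoms: "patients who receive disallowed concomitant medication will be censored at the last time at which the patient had an Overall VAS score" before the drug. There is a special case: "If this is Presentation and hence prior to study drug administration then the time to minimal symptoms will be censored at time 0 minutes". SAP 4.1.4.5 does the same for complete resolution (exploratory): "The time to complete resolution of symptoms for patients who receive disallowed concomitant medication will be censored at the last time the patient" had a VAS score before the drug.

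SAP 6.7.4 then states: "Kaplan-Meier (KM) analyses will be performed for each of the time to event endpoints". It adds the number and percentage of patients with the event, and the median and quartiles with 95% confidence intervals.

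Protocol 8.2.2 lists when additional treatment may be given. The list includes "Clear progression of symptom severity, with or without the occurrence of symptoms at new angioedema locations", "Unacceptable degree of abdominal pain", life-threatening symptoms, and adverse events that need treatment. It goes on: "In case of therapeutic failure, rescue therapies (such as pdC1INH) or fresh frozen plasma may be administered". Both of those products are on the disallowed list in SAP 4.1.1.6.

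Therapeutic failure (SAP 4.1.4.6) counts a listed drug only if it is taken before initial relief.

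**The concern.** Kaplan-Meier assumes that a censored attack would have gone on to recover like the attacks still under observation. An attack rescued because it is progressing or too painful is not like those. After rescue, recovery on Ruconest alone can no longer be observed.

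An attack rescued between dosing and the 30-minute VAS has Presentation as its last score. It is censored at 0 minutes and adds nothing to the curve, although such attacks may be among the worst.

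The rule also runs against the caution found elsewhere in the SAP. Section 4.1.3.1 fills missing VAS scores with the worse neighbouring value, and 5.5.1 assumes no event when data are insufficient. Known rescue gets the more favourable handling.

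At stake are the curve and quartiles for one secondary and three exploratory endpoints, in an uncontrolled study of about 20 children.

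**Working it through.** **Inputs from the documents.** VAS times after dosing are 0.5, 1, 2, 4, 8 and 24 h (Protocol 10.2.3). The target is 20 treated patients (Protocol 7.5). Earlier median times to minimal symptoms are 4 h in C1 1202/1203 and 480 min in the C1 1304 RCT at 100 U/kg (Protocol 9.3). There is no rescue rate, and no figure of the plan's own to reproduce.

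**Direction.** At each event time Kaplan-Meier multiplies by 1 − d/n, where d is events and n is attacks at risk. Censoring a rescued attack lowers later values of n and leaves d unchanged. So 1 − KM can never be below the curve that keeps the attack in the risk set without the event.

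**Size, closed form.** Assume exponential times with median m, so S(t) = 2^(−t/m). Assume rescue just after the 4 h VAS, drawn at random from event-free attacks, with r the rescued share of all attacks.

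- Censoring: 1 − KM(24) = 1 − S(24).
- Rescue as competing event: C(24) = [1 − S(4)] + [S(4) − r] × [1 − S(24)/S(4)].

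Median 4 h: S(4) = 0.5 and S(24) = 0.0156, so 1 − KM = 98.4%. With r = 0.10, C = 0.5 + 0.4 × 0.96875 = 88.8%.

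Median 8 h: S(4) = 0.7071 and S(24) = 0.125, so 1 − KM = 87.5%. With r = 0.20, C = 0.2929 + 0.5071 × 0.8232 = 71.0%.

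If the percentage p applies only to attacks event-free at 4 h, then r = p × S(4). For p = 0.20 and median 8 h, r = 0.1414 and C = 0.2929 + 0.5657 × 0.8232 = 75.9%.

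| Median | 1 − KM at 24 h | C, 5/10/20% of all attacks | C, 5/10/20% of event-free attacks |
|---|---|---|---|
| 4 h | 98.4% | 93.6 / 88.8 / 79.1% | 96.0 / 93.6 / 88.8% |
| 8 h | 87.5% | 83.4 / 79.3 / 71.0% | 84.6 / 81.7 / 75.9% |

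With SE = √(C(1 − C)/20), the gaps for shares of all attacks are 0.9, 1.4 and 2.1 SE (median 4 h) and 0.5, 0.9 and 1.6 SE (median 8 h). For shares of event-free attacks they run from 0.5 to 1.4 SE and from 0.4 to 1.2 SE.

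**Exact example with 20 attacks (assumed data).** There are 2 events at 2 h, 4 at 4 h and 6 at 8 h. One unrescued attack has no event, k attacks are rescued after the 2 h VAS, and the rest have the event at 24 h. At 24 h, 1 − KM = 1 − 0.9/(18 − k), against (19 − k)/20 with rescue as non-response. At 8 h, 1 − KM = 1 − 0.9(8 − k)/(18 − k), against 12/20 = 60%.

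| k | 8 h, censored | 24 h, censored | 24 h, non-response |
|---|---|---|---|
| 1 | 62.9% | 94.7% | 90.0% |
| 2 | 66.2% | 94.4% | 85.0% |
| 4 | 74.3% | 93.6% | 75.0% |
| 6 | 85.0% | 92.5% | 65.0% |

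The median is 480 min on both rules for every k shown.

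**Bias against the no-rescue outcome.** The closed form draws rescue at random, so there KM recovers the no-rescue share exactly. Its gap is the distance between censoring and non-response. A simulation let the slowest attacks be the rescued ones (lognormal times, median 480 min, assumed log-SD 1, rescue after the 2 h VAS). With 5%, 10% and 20% of all attacks rescued, KM at 24 h was 90.8%, 96.0% and 100%, against no-rescue shares of 86.3%, 86.5% and 86.2%. With random rescue of 20%, KM was 86.3% against 86.4%, while rescue as non-response gave 69.3%.

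**The case against.** The strongest reply is that censoring at rescue answers a legitimate question, namely recovery had no rescue been given, and that the planned outputs already disclose most of the difference. Neither document names an estimand. If follow-up is otherwise complete, the crude event percentage in SAP 6.7.4 equals the 24 h cumulative incidence. Therapeutic failure is tabulated with reasons, and event times and concomitant medications are listed. This stands, but only in part. The crude percentage does not correct the curve or the quartiles. A listed drug taken after beginning of relief and before the event is not a failure on the medication criterion. And KM answers the no-rescue question only if rescue is unrelated to prognosis.

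Not all rescue signals poor response. Protocol 8.2.2 also covers adverse events and allows pain medication and anti-emetics as needed, and the disallowed list includes any analgesic or anti-emetic apart from the paracetamol exception. A second Ruconest dose, the recommended first rescue, is not on the SAP list and is not censored. This stands, so the link to poor response holds for most rescue, not all.

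A reader might infer that the main efficacy display is affected. It is not: the primary efficacy measure is time to beginning of relief by VAS (SAP 4.1.2.1), which has no rescue censoring. Efficacy is a secondary objective, and SAP 5.2 plans no hypothesis test, so no error rate is at issue.

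A reader might also infer that the upper quartile would be lost at a 20% rescue rate with an 8 h median. That holds if 20% of all attacks are rescued (71.0%, below 75%), but not if 20% of event-free attacks are (75.9%).

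**Conclusion.** The point holds at moderate weight. For time to minimal symptoms (VAS, IS, TEQ) and complete resolution, the censoring is informative, and the Kaplan-Meier curve and quartiles are at or above their values with rescue as non-response. The direction is certain for that comparison. It holds against the no-rescue outcome as well if rescued attacks are the slowest. It need not hold against a reading that credits recovery after rescue.

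The size rests on assumed rescue rates and timing. At 24 h the gap is about 2 to 12 points if 5 to 20% of event-free attacks are rescued, and about 4 to 19 points if those are shares of all attacks. One rescued attack in the 20-attack example costs about 5 points. The modelled rescue just after 4 h cannot affect the IS endpoint, where scoring ends at 4 h; only earlier rescue can.

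The closed-form gaps should not be read as bias from slow attacks, since rescue was random there. Nor do the documents support saying that the medians are overstated, because the median may stay put on this grid.

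**What to change.** In SAP 4.1.3.1, 4.1.4.2, 4.1.4.4 and 4.1.4.5, limit the rule to listed drugs given after study drug and before the event. Treat that use as a competing event, with Aalen-Johansen cumulative incidence and quartiles read from it. Alternatively, keep the attack event-free to a stated horizon: 24 h for VAS and TEQ, 4 h for IS, 72 h for complete resolution. Report the existing censored Kaplan-Meier beside it as a sensitivity analysis. Handle pre-dose use separately as an eligibility deviation.

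Two definitions should be settled at the same time. State whether listed drugs taken more than 8 h after dosing count, since Protocol 8.2.2 restricts them only up to 8 h. Also reconcile Protocol Appendix F, which lists recombinant C1 inhibitor among the failure medications, with Protocol 8.2.2, which excludes Ruconest.

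The cost is SAP wording and recoded times from data already collected. Reported times become slightly less favourable. A minor analgesic or anti-emetic would count as non-response, and the retained censored curve shows how much that matters. The SOP deviation form attached to the SAP says the analysis is finalised, so this would be an added analysis, described and justified in the CSR as SAP 7.5 provides for changes after database lock.

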#### **4.1.4 Exploratory Efficacy Measures**

##### **4.1.4.1 Time to beginning of relief based on IS score**

The time to beginning of relief will be assessed using the IS scores, where time of beginning of relief will be assessed as the first time point at which the investigator assesses the severity of an attack as at least one point less (IS decreased by at least 1 point) compared to Baseline at any eligible location.

Patients who do not have beginning of relief during the time that they are followed-up will be censored at the last time at which the IS score is recorded for any eligible location. Note: If a patient was randomized but did not have any post-baseline efficacy data then they will be censored at Presentation.

Time to beginning of relief (minutes) will be calculated as:

Actual date and time of first relief (or date and time of censoring) – Date and time of the Baseline IS assessment

The actual date and time of beginning of relief will be used in the calculation.

##### **4.1.4.2 Time to minimal symptoms based on IS score**

The time of minimal symptoms for an attack using the assessment by the investigator is defined as the time at which the IS at the last location falls to 1 point or below.

The time to minimal symptoms for an attack assessed using the IS scores will be assessed for all locations where IS scores are recorded.

- Patients who do not have minimal symptoms during the time that they are followed-up will be censored at the last time at which the IS score is recorded. Note: If a patient was randomized but did not have any post-baseline efficacy data then they will be censored at Presentation.
- A worst-case scenario will be used to impute missing IS scores for locations. If there are 2 non-missing values either side of missing value(s) then LOCF or NOCB will be used to carry forward or back the largest IS score. If there is only one IS score followed by missing values or after missing values it will be carried forward or back. If the IS score for a location is blank at Baseline, but then the location is affected by angioedema post-dosing, a score of 0 will be imputed for all post-baseline time-points up until the first

documented IS score. The worst-case scenario method will then be applied for all subsequent missing IS scores.

- The time to minimal symptoms for patients who receive disallowed concomitant medication will be censored at the last time at which the patient had an Overall VAS score prior to their receipt of disallowed concomitant medication. If this is Presentation and hence prior to study drug administration then the time to minimal symptoms will be censored at time 0 minutes.

Time to minimal symptoms (minutes) will be calculated as:

Actual date and time of minimal symptoms (or date and time of censoring) – Date and time of the IS assessment at Baseline

The actual date and time of minimal symptoms will be used in the calculation.

#### **4.1.4.3 Time to beginning of relief based on TEQ**

Time to beginning of relief of symptoms (TEQ) is assessed using Questions 1 and 2 of the TEQ at the most severe eligible location. The time of relief will be the first time point at which the response to Question 1 of the TEQ was 'A Little Better', 'Better' or 'Much Better' AND the response to Question 2 of the TEQ was 'Yes' with persistence of the improvement at the next time point AND the response to Question 2 of the TEQ was 'Yes'). Persistence of the improvement at the next time point can be defined to mean that at the next available time point, the response to Question 1 of the TEQ was at least as good as the previous response (e.g. if the previous response was 'Better' then the subsequent response would have to be 'Better' or 'Much Better', 'A Little Better' would not be sufficient)

The time of relief of symptoms will be the first time point at which Question 1 of the TEQ was 'A Little Better', 'Better' or 'Much Better' AND the response to Question 2 of the TEQ was 'Yes'. For example, if this was achieved at 2 hours with persistence shown at 4 hours then the time of beginning of relief of symptoms will be 2 hours.

In addition, any patient who did not have beginning of relief of symptoms during the time that they are followed-up will be censored at the last time at which the TEQ is recorded for the primary attack location. Note: If a patient was randomized but did not have any post-baseline efficacy data then they will be censored at Presentation.

Patients who do not have a response of 'A Little Better', 'Better' or 'Much Better' to Question 1 of the TEQ and a response of 'Yes' to Question 2 of the TEQ until the last time the TEQ was recorded will not have achieved beginning of relief with persistence. Therefore, they will be censored at the penultimate time that the TEQ was recorded.

Time to beginning of relief of symptoms (minutes) will be calculated as:

Actual date and time of first relief of symptoms (or date and time of censoring) – Date and time of first Study Drug Administration

The actual date and time of beginning of relief of symptoms will be used in the calculation.

To allow for missing data in the calculation of time to beginning of relief of symptoms the following rules will be applied. These will ensure that for each patient a conservative approach to estimating missing data is used:

- If a patient has a response of 'A Little Better', 'Better' or 'Much Better' to Question 1 of the TEQ with a missing response to Question 2 of the TEQ then the response to Question 2 will be imputed as 'Yes' if the previous response to Question 2 of the TEQ was 'Yes' and the next response to Question 2 of the TEQ is 'Yes', or else will be imputed as 'No' if either the previous or subsequent responses are not missing.
- If a patient has a response of 'Yes' to Question 2 of the TEQ with a missing response to Question 1 of the TEQ then the response to Question 1 will be imputed as the worst response of the previous and subsequent responses to Question 1.

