10.1.3 Other study parameters

Safety variables after single and repeat treatment that will be subject to exploratory analysis:

- vital signs
- ECG
- Routine clinical laboratory parameters

Efficacy variables that will be subject to exploratory analysis:

- time to beginning of relief based on questions 1 and 2 of the TEQ, defined as the first time-point at which Question 1 is answered as a little better, better or much better and Question 2

Safety of Ruconest in 2-13 year old HAE patients

is answered as yes for the most severe eligible location, with persistence of these responses at the next time point.

- time to minimal symptoms on the basis of Question 3 of the TEQ, defined as the first time-point at which Question 3 is answered as yes for all locations
- time to complete resolution based on the time-point at which all symptoms at all locations have resolved
- therapeutic failure: A patient will be assessed as having had a therapeutic failure if any of the following occurs:
 - time to the beginning of relief of symptoms for the attack based on the overall VAS occurs later than 4 hours after baseline
 - within 4 hours after beginning of treatment administration and after beginning of relief the overall VAS increases again to a value of at least the baseline score
 - the patient has occurrence of HAE at a new location within 4 hours after achieving beginning of relief of symptoms
 - the patient taking any of the medications that may interfere with the assessment of the impact of Ruconest on efficacy measures, between the onset of the attack and prior to time of initial relief of symptoms including:
 - Narcotics
 - plasma-derived C1 inhibitor
 - Fresh frozen plasma
 - Bradykinin receptor antagonist
 - Analgesics
 - Anti-emetics
 - Non Steroidal Anti-Inflammatory Drugs (NSAIDs)

Any change in current and optional maintenance therapy (androgens and/or anti-fibrinolytics) from the time of the onset of the current attack is not allowed. The dosage of androgens and anti-fibrinolytics may not be increased earlier than 24 hours after the treatment with study medication.

For a detailed description and definition of used terms, see [Appendix F](#).

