12.2 Variables

The following data will be considered in the analysis:

Safety

- immunogenicity data
- adverse events
- laboratory data (hematology, biochemistry).
- vital signs
- ECG

Efficacy

- time to beginning of relief on the basis of the overall severity VAS using the first time-point with a decrease of at least 20 mm at any eligible location, with persistence at the next time-point
- time to minimal symptoms assessed by using the overall severity VAS, defined as the first time point at which the overall severity VAS fall below 20 mm for all assessed locations
- time to beginning of relief on the basis of the IS using the first time-point with a decrease of at least one point at any eligible location
- time to minimal symptoms on the basis of the first time-point at which the IS reaches a value of one or less at all locations
- Time to beginning of relief on the basis of Question 1 and 2 of the TEQ, defined as the first time-point at which Question 1 is answered as a little better, better or much better and

Question 2 is answered as yes for the most severe eligible location, with persistence of these responses at the next time point

- Time to minimal symptoms on the basis of Question 3 of the TEQ, defined as the first time-point at which Question 3 is answered as yes for all locations
- time to complete resolution based on the time-point at which all symptoms at all locations have resolved
- therapeutic failure

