#### **4.1.1 Definitions**

##### **4.1.1.1 Treatment Effect Questionnaire (TEQ)**

TEQ responses are recorded repeatedly throughout the study at the following time-points; Presentation (Pre-dose) and after treatment at 30 minutes, 1, 2, 4, 8 and 24 hours.

The TEQ responses are measured at up to five different locations (Abdominal, Oro-pharyngeal and/or Laryngeal (OPL), Facial, Urogenital or Peripheral), depending on the affected locations.

The TEQ consists of the following questions:

- Question 1
  - Pre-dose – To what extent has the overall severity of your [abdominal] HAE attack changed since your arrival at the study center?
  - After treatment – To what extent has the overall severity of your [abdominal] HAE attack changed since you received the infusion?
  - Possible responses are 'Much Worse', 'Worse', 'A Little Worse', 'Not Changed', 'A Little Better', 'Better' or 'Much Better'.
- Question 2
  - Pre-dose – Overall, has the intensity of your [abdominal] HAE attack symptoms begun to decrease noticeably since your arrival at the study center?
  - After treatment – Overall, has the intensity of your [abdominal] HAE attack symptoms begun to decrease noticeably since you received the infusion?
  - Possible responses are 'Yes' or 'No'.
- Question 3

- At this moment, are your [abdominal] HAE attack symptoms minimal (barely noticeable)?
- Possible responses are 'Yes' or 'No'.

 abdominal is replaced by the relevant attack location.

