## 7. Changes to the Planned Analyses

### 7.1 Changes to the Analyses Described in the Study Protocol and Protocol Amendments

Due to an inadequate number of sampling time points; the only PK parameters calculated will be AUC0-3 and  $C_{max}$ . See Section 7.3 for further details.

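### The SAP's persistence rule for TEQ relief is stricter than the protocol's and is not declared, so some children who are still improved get a later relief time or are censored

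*SAP*

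**What the plan says.** **Protocol.** Sections 10.1.3 and 12.2 define TEQ relief in the same terms. In 12.2 the event is the first time point at which "Question 1 is answered as a little better, better or much better and" Question 2 is answered yes, at the most severe eligible location. Section 10.1.3 gives the persistence condition as "with persistence of these responses at the next time point". Neither section compares the grade of the second answer with the grade of the first.

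**SAP.** Section 4.1.4.3 keeps the same qualifying answers and still needs Question 2 to be yes. It adds that at the next available time point "the response to Question 1 of the TEQ was at least as good as the previous response". Its illustration starts from *Better*, after which "A Little Better' would not be sufficient". A second example, with times in hours, fixes the timing: "if this was achieved at 2 hours with persistence shown at 4 hours then the time of beginning of relief of symptoms will be 2".

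**The question itself.** SAP 4.1.1.1 and Protocol Appendix C show that the post-dose Question 1 asks how far the overall severity of the "HAE attack changed since you received the infusion". The reference point is the infusion, not the previous form.

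**Declared changes.** SAP 7.1 lists one departure from the protocol analyses: "Due to an inadequate number of sampling time points; the only PK parameters calculated will be" an AUC and a C_max. The TEQ rule is not mentioned. SAP 7.3 records only that Section 4.1 was expanded with more detail since SAP version 2.0.0.

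**The concern.** The endpoint is the *beginning* of relief, and persistence is there to screen out a transient answer. A child who says *Much better* on one form and *Better* on the next has reported improvement since the infusion both times. Relief has begun and is still present. The protocol accepts that pair and the SAP rejects it.

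The SAP rule also differs from the one used for the VAS. Protocol Appendix F and SAP 4.1.2.1 require the next VAS value to remain at least 20 mm below baseline and do not compare it with the previous value. A child whose VAS fall shrinks from 60 mm to 40 mm keeps the earlier VAS relief time, while the same pattern on the TEQ loses it. Table 14.2.1.5.1 shows VAS, IS and TEQ relief times together, so a reader would take the VAS and TEQ persistence rules to be alike.

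At stake is whether the reported TEQ relief time is the one the protocol defines. Because the change is not declared, a reader of the results would assume that it is.

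**Working it through.** **Inputs**
- Post-dose TEQ times: 0.5, 1, 2, 4, 8 and 24 h (SAP 4.1.1.1).
- Improved answers to Question 1, in order: *A little better* < *Better* < *Much better*.
- Protocol rule: relief is at time *i* if answer *i* is improved and answer *i+1* is improved.
- SAP rule: relief is at time *i* if answer *i* is improved and answer *i+1* ≥ answer *i*.
- Assumptions: Question 2 is yes whenever Question 1 is improved, and no form is missing.

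**Step 1: the SAP's own example.** *Better* at 2 h and *Better* from 4 h onward gives 2 h under both rules, which reproduces the SAP's figure.

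**Step 2: pairs of improved answers.** There are 3 × 3 = 9 ordered pairs. All 9 persist under the protocol.

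| First answer | Next answers accepted by the SAP | Rejected |
|---|---|---|
| A little better | all 3 | 0 |
| Better | Better, Much better | 1 |
| Much better | Much better only | 2 |

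The SAP accepts 3 + 2 + 1 = 6 and rejects 3: *Better* to *A little better*, *Much better* to *A little better*, and *Much better* to *Better*.

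**Step 3: effect on the time.** In each row there is no improvement before the first time shown.

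| Answers to Question 1 | Protocol | SAP |
|---|---|---|
| Much better 30 min, Better 1 h, Better 2 h | 30 min | 60 min |
| Much better 1 h, Better from 2 h on | 1 h | 2 h |
| Much better 4 h, Better 8 h, Better 24 h | 4 h | 8 h |
| Much better 1 h, Better 2 h, A little better from 4 h on | 1 h | 4 h |
| Much better 8 h, Better 24 h | 8 h | no event, censored |

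The last row depends on 8 h being the first improvement. If an earlier pair had qualified, that earlier time would stand under both rules. In general, a decline that comes after a pair the SAP has already accepted changes nothing.

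**Step 4: direction.** Give Question 1 four levels (not better, plus the three improved grades) at six times. There are 4^6 = 4,096 possible sequences. The two rules disagree in 1,293. The SAP yields no event in 259 of these, a later time in 1,293 − 259 = 1,034, and an earlier time in none. This follows from the definitions, since every pair the SAP accepts is also accepted by the protocol. These are counts of possible patterns, not expected frequencies in patients.

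**The case against.** **The endpoint carries little weight.** TEQ relief is exploratory in Protocol 10.1.3 and in SAP 4.1.4. The primary objective is safety, the primary efficacy measure is the VAS, and therapeutic failure (SAP 4.1.4.6) is judged on VAS relief. SAP 5.2 plans no hypothesis test. The stricter rule can only make TEQ relief look slower, so it cannot flatter the product. All of this stands and sets the severity.

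**The protocol wording leaves some room.** Its persistence phrase could mean that the level of improvement must hold, and the protocol leaves detail to the SAP. This stands in part: a stricter rule is a defensible choice if it is disclosed. Reading the phrase as requiring the identical answer would fail a child who goes from *A little better* to *Better*, and the SAP does not adopt that reading either. Persistence of the qualifying set is the more natural meaning, fits a question anchored to the infusion, and matches the VAS rule.

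**Stronger readings that the documents do not support.** A reader might infer that the delay is largest for the best responders, because the test is hardest after *Much better*. That is not shown: a child who stays at *Much better* is unaffected, and those affected are children whose reported benefit partly wanes within the improved range. A reader might also take 3 of 9 as one child in three. The pairs are not equally likely, and the documents give no frequencies.

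**Conclusion.** The point holds, as a minor one. SAP 4.1.4.3 adds a condition to TEQ persistence that Protocol 10.1.3 and 12.2 do not contain, and SAP 7.1 does not declare it. For an attack whose Question 1 answer falls within the improved range before any pair has met the SAP rule, TEQ relief moves later or is censored. It never moves earlier.

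The number of children affected, and so any shift in a median, cannot be estimated from the documents and could be nil. The primary safety objective, the VAS endpoints and therapeutic failure are untouched. The conclusion rests on reading the protocol's persistence phrase as the qualifying set of answers continuing to hold. The times in the working also assume that Question 2 is yes with every improved answer and that no form is missing.

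**What to change.** **Preferred.** Define persistence as in the protocol: at the next available TEQ, Question 1 is in any of the three improved categories and Question 2 is yes. Re-derive the TEQ relief times in Tables 14.2.1.5.1 (ITT) and 14.2.1.5.2 (PP) and in Figure 14.2.1.5.

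**If the stricter rule is kept.** Declare it as a change from the protocol, give the reason, and report the protocol-defined TEQ time beside it.

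**Cost.** One sentence of SAP text plus the re-derivation of one exploratory endpoint. No new data are needed, because the individual TEQ answers are already held and listed (Listing 16.2.6.1.2). The SOP deviation form attached to the SAP says that the analysis is finalised, so the change would be described and justified in the clinical study report, the route that SAP 7.5 provides for changes after database lock.
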